9.3 Replacement of Patients

For Part A, patients will be replaced if they have received less than 67% dose intensity [(administered dose in mg/planned dose in mg) × 100] of ARRY-382 or if they did not receive pembrolizumab for any reason other than an AE or abnormal laboratory value that is not related to disease, disease progression, intercurrent illness or concomitant medications/therapies before completing Cycle 1.

For the Phase 2 PD-1/PD-L1 Inhibitor Refractory cohort, patients who discontinue prior to study completion will not be replaced.

For the Phase 2 prOVCA and PDA cohorts, additional patients will be enrolled to account for those who are found to be MSI-H/dMMR in order to evaluate the targeted patient population and to satisfy the Simon's 2-stage design.

10.0 SAFETY MONITORING: DEFINITIONS AND REPORTING

10.1 Adverse Event

An AE is defined as any untoward medical occurrence, including the exacerbation of a pre-existing condition, in a patient administered an investigational (medicinal) product and that does not necessarily have a causal relationship with this treatment. An AE can therefore be any unfavorable and unintended sign (such as an abnormal laboratory finding), symptom, or disease temporally associated with the use of investigational product, whether or not considered related to the investigational product.

10.1.1 Events Related to Progression of Disease

Progression of malignancy (including fatal outcomes), if documented by use of appropriate method (for example, as per RECIST criteria for solid tumors) will be designated as progression of disease in the eCRF and should not be reported as an AE or SAE unless a causal relationship to study drug is suspected.

10.1.2 Clinical Laboratory Abnormalities

An abnormal laboratory value that is not associated with an already reported AE is to be recorded as an AE only if an action on the study drug is made as a result of the abnormality, if intervention for management of the abnormality is required, or at the discretion of the Investigator.

Laboratory abnormalities that meet the criteria for AEs should be followed until they have returned to normal or baseline, or per Investigator discretion.

10.1.3 Overdose

An overdose of study drug (whether symptomatic or asymptomatic) will be reported as an AE.

10.2 Assessment of Severity

The severity rating of an AE refers to its intensity. The severity of each AE will be determined by the Investigator using the National Cancer Institute (NCI) CTCAE, version 4.03 ([US Department of Health and Human Services 2010](#)). For any term that is not specifically listed in the CTCAE scale, severity should be assigned a grade of 1 through 5 using the following CTCAE guidelines:

Grade 1: Mild; asymptomatic or mild symptoms; clinical or diagnostic observations only; intervention not indicated

Grade 2: Moderate; minimal, local or noninvasive intervention indicated; limiting age-appropriate instrumental activities of daily living

Grade 3: Severe or medically significant but not immediately life-threatening; hospitalization or prolongation of hospitalization indicated; disabling; limiting self-care activities of daily living

Grade 4: Life-threatening consequences; urgent intervention indicated

Grade 5: Fatal

10.3 Assessment of Causality

An assessment of causal relationship of study drug to each AE must be performed by the Investigator. Medical judgment should be used to determine the cause of the AE, considering all relevant factors such as (but not limited to) the underlying study indication, coexisting disease, concomitant medication, relevant history, pattern of the AE, temporal relationship to the study medication and de-challenge or re-challenge.

Yes (possibly, probably or definitely related): there is a reasonable possibility that the study drug caused the event; 1 or more of the following criteria apply:

- The event follows a reasonable temporal sequence from administration of study drug.
- The event could not be reasonably attributed to the known characteristics of the patient's clinical state, environmental or toxic factors or other modes of therapy administered to the patient.
- The event follows a known pattern of response to study drug.
- The event disappears or decreases on cessation or reduction in dose of the study drug. (It should be noted that in some situations an AE will not disappear or decrease in intensity upon discontinuation of study drug despite other clear indications of relatedness).
- The event reappears or worsens when the study drug is re-administered.

No (unlikely, probably not related or definitely not related): there is no reasonable possibility that the study drug caused the event; 1 or more of the following criteria apply:

- The event does not follow a reasonable temporal sequence from administration of study drug.

- The event could be reasonably attributed to the known characteristics of the patient's clinical state, concurrent illness, environment or toxic factors or other modes of therapy administered to the patient.
- The event does not follow a known pattern of response to study drug.
- The event does not disappear or decrease on cessation or reduction in dose of the study drug, and it does not reappear or worsen when the study drug is re-administered.

10.4 Assessment of Seriousness

An AE is considered “serious” if it results in any of the following outcomes:

- Results in death
 - Death is an outcome of an SAE and not an SAE in itself. When death is an outcome, the event(s) resulting in death should be reported (e.g., “pulmonary embolism” with a fatal outcome) and assigned severity Grade 5.
 - Death should only be reported as an SAE term when no additional information is known about a fatal event.
- Is immediately life-threatening (its occurrence places the patient at immediate risk of death. It does not include an event that, had it occurred in a more severe form, might have caused death)
- Requires inpatient hospitalization or prolongation of existing hospitalization

Note: Hospitalization includes any hospital admission, even if for less than 24 hours. The following do not meet hospitalization serious criteria:

- A visit to the emergency room, or outpatient observation that does not result in admission
- Elective surgery, planned prior to signing consent
- Routine health assessment requiring admission
- Results in a persistent or significant incapacity or substantial disruption of the ability to conduct normal life functions
- Is a congenital anomaly/birth defect
- Based upon appropriate medical judgment, represents an important medical event that may jeopardize the patient or may require intervention to prevent one of the outcomes described above

10.5 Reporting of Serious and Nonserious Adverse Events

All AEs, serious and nonserious (including the exacerbation of a pre-existing condition) and regardless of causality to study drug will be fully recorded on the appropriate eCRF. For each AE, the Investigator must provide its duration (start and end dates or ongoing), severity (intensity), assessment of causality, whether specific action or therapy was required, and whether action was taken with regard to study drug treatment.

Any AE that occurs from the signing of the informed consent until the first dose of study drug is to be recorded on the AE eCRF only if the event was related to a study procedure. All other AEs/findings prior to the first dose of study drug should be recorded on the medical history eCRF. All AEs occurring from the first dose of study drug until 30 days after the last dose of study drug must be recorded on the AE eCRF, regardless of causal relationship to investigational product. SAEs occurring greater than 30 days after the last dose of study drug should be reported only if considered related to investigational product.

In addition to recording SAEs on the AE eCRF, all SAEs must be reported to the Sponsor within 24 hours of the Investigator's knowledge by faxing the completed SAE form to the Sponsor at the number provided on the SAE form or fax cover sheet. If new information becomes available for a previously reported SAE, a follow-up SAE report should be sent within 24 hours.

Investigators must follow patients with AEs/SAEs until the event has resolved, the condition has stabilized, withdrawal of consent, the patient is lost to follow-up or death OR until 30 days after the last dose of study drug, whichever occurs first. Ongoing treatment-related SAEs may be followed beyond this time period if clinically indicated.

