5.3 Contraception

Female patients of childbearing potential must agree to use acceptable or highly effective methods of contraception to avoid pregnancy for the duration of study treatment through 5.5 months after the last dose of pembrolizumab (i.e., 30 days [duration of ovulatory cycle] plus the time required for the investigational drug to undergo approximately 5 half-lives).

Non-sterile male patients who are sexually active with female partners of childbearing potential must agree to use acceptable or highly effective methods of contraception to avoid fathering a child for the duration of study treatment and for 7.5 months after the last dose of pembrolizumab

(i.e., 90 days [duration of sperm turnover] plus the time required for the investigational drug to undergo approximately 5 half-lives).

The permitted contraceptive methods listed below ([CTFG Guidelines 2014](#)) should be communicated to the patients and their understanding confirmed.

The following methods have been determined to be highly effective (i.e., can achieve a failure rate < 1% per year when used consistently and correctly):

- Complete abstinence from heterosexual intercourse during the entire period of risk associated with the study treatments; the reliability of sexual abstinence should be evaluated in relation to the duration of the clinical trial and the preferred and usual lifestyle of the patient
- Combined (estrogen and progestogen containing) hormonal contraception associated with inhibition of ovulation:
 - Oral
 - Intravaginal
 - Transdermal
- Progestogen-only hormonal contraception associated with inhibition of ovulation:
 - Oral
 - Injectable
 - Implantable
- Intrauterine device (IUD)
- Intrauterine hormone-releasing system (IUS)
- Bilateral tubal occlusion
- Vasectomized partner (considered highly effective provided the vasectomized male has received medical assessment of surgical success and that the male is a female patient's sole sexual partner)

Acceptable birth control methods that result in a failure rate of more than 1% per year include:

- Progestogen-only oral hormonal contraception, where inhibition of ovulation is not the primary mode of action
- Male or female condom with or without spermicide
- Cap, diaphragm or sponge with spermicide

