ALT or AST elevations	
 • ALT or AST > 8 × ULN ≤ 20 × ULN (Grade 3) 
 ○ Withhold ARRY-382. Resume treatment at the next lower dose level if ALT or AST resolves to Grade 1 or baseline (or ≤ 5 × ULN in presence of liver metastases) in ≤ 7 days ○ Discontinue ARRY-382 if ALT or AST > 8 × ULN for > 7 days • ALT or AST ≥ 5 × ULN and ≤ 8 × ULN (Grade 3) 
 ○ Withhold ARRY-382. Resume treatment at the next lower dose level if ALT or AST resolves to Grade 1 or baseline in ≤ 14 days ○ Discontinue ARRY-382 if ALT or AST > 5 × ULN for > 14 days • ALT or AST > 3 × ULN and bilirubin levels ≥ 2 × ULN or an INR > 1.5 unless clearly attributable to disease progression 
 ○ Discontinue ARRY-382 • ALT or AST > 20 × ULN (Grade 4) 
 ○ Discontinue ARRY-382

AE = adverse event; ALT = alanine aminotransferase; AST = aspartate aminotransferase; CK = creatine kinase; ECG = electrocardiogram; INR = international normalized ratio; irAE = immune-related adverse event; QTcF = QT interval corrected for heart rate using Fridericia's formula; ULN = upper limit of normal

- ^a The following exceptions apply: 1) ARRY-382 should not be withheld for increased CK unless it is associated with an increase in creatinine $\geq 1.5 \times$ the baseline value for creatinine OR until the CK increase remains \geq Grade 3 for > 7 days. 2) In the event of Grade 3 nausea, vomiting or diarrhea, the patient can continue at the same dose of ARRY-382 if the patient is responsive to treatment measures.
- ^b A patient with a Grade 4 AE may resume treatment at the next lower dose level if the AE recovers to Grade 0 or 1 and, if in the opinion of the Investigator and Sponsor, the patient can be monitored for recurrence of AE.

Patients should be evaluated weekly, at a minimum for nonlaboratory, ARRY-382-related toxicities until resolution or return to baseline, and then at least monthly until return to baseline, whichever comes first. For abnormal laboratory values that qualify as AEs, patients should be followed twice weekly until resolution or return to baseline.

Doses of ARRY-382 withheld during a cycle will not be made up. When a dose reduction is required because of AEs, no dose re-escalation will be permitted for the duration of study treatment.

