^c Measurement of CK isoenzymes and urine myoglobin only necessary if total CK is \geq Grade 2, unless there are cardiac signs and symptoms. If cardiac signs and symptoms are present, measure CK isoenzymes and urine myoglobin if total CK is any grade above normal.

Site-specific handling instructions for hematology, coagulation, clinical chemistry, thyroid panel, and urinalysis samples should be followed. Screening results will be assessed by the Investigator to determine patient eligibility. Day 1 results (or assessments allowed within 96 hours prior to Day 1) will be assessed by the Investigator prior to first dose of study treatment; clinical chemistry and coagulation test results must be reviewed before the first dose of study drug is administered in each cycle. Additional clinical laboratory tests may be obtained at any time during the study at the Investigator's discretion. Clinically significant findings should be followed to resolution or stabilization.

Blood and urine sample collections on dosing days must be performed prior to study treatment administration. Laboratory test results required to make decisions regarding potential dose modifications (as specified in [Section 6.3](#)) should be reviewed prior to study treatment administration.

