8.2.2.2.2 Subsequent Cycles Day 15 (± 2 Days)*

- Blood sample for the clinical chemistry and hematology (Cycles 2, 3, and 4 only)
- Administration/dispensing of ARRY-382
- Review of concomitant medications

- Review of AEs

* For Cycles ≥ 5 , on each Day 15 where only AEs and concomitant medications are assessed, a telephone call to the patient can substitute for a clinical visit. However, if the Investigator feels that there are AEs that need to be further assessed, a clinic visit may be warranted.

8.3 Treatment Discontinuation Visit (to be completed within 2 weeks after treatment discontinuation or prior to the initiation of subsequent anticancer therapy, whichever occurs first)

- ECOG PS
- Physical exam, including body weight
- Vital signs, including blood pressure, pulse, and temperature
- Single 12-lead ECG
- Serum or urine pregnancy test (females of childbearing potential only)
- Blood sample for the following tests:
 - Clinical chemistry, thyroid panel, hematology, and coagulation

- Urine sample for the following tests:
 - Urinalysis

- Review of concomitant medications
- Review of AEs

8.4 30-Day (\pm 3 Days) Safety Follow-up Visit

All patients will return for a 30-Day Safety Follow-up Visit approximately 30 days after the last dose of study treatment or prior to the initiation of subsequent anticancer therapy, whichever occurs first.

- ECOG PS
- Physical exam, including body weight
- Vital signs, including blood pressure, pulse, and temperature
- Serum or urine pregnancy test (females of childbearing potential only)
- Blood sample for the following tests:
 - Clinical chemistry, thyroid panel, hematology, and coagulation
- Urine sample for urinalysis
- Review of AEs

Additional safety assessments may be performed to monitor any safety concerns identified at the treatment discontinuation visit. If the treatment discontinuation visit was performed \geq 21 days from last dose of study drug, the 30-day safety follow-up visit does not need to be performed.

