### 7.6.4 Adverse Events

AEs and serious adverse events (SAEs) will be coded by PT and SOC using the latest available MedDRA version.

The severity of an AE will be assessed by the investigator using the NCI CTCAE, Version 4.03. For patients with more than 1 AE within a SOC or PT, only the highest grade will be included in by-severity summaries.

The investigator will also assess whether the AE is suspected to be related to study drug (i.e., a treatment-related AE). For patients with more than 1 AE within a SOC or PT, the highest level of relationship (related is higher than not related) will be included in the by-relationship summaries.

For summaries by SOC and PT, each patient will be counted at most once per SOC and at most once per PT. For summaries by PT, each patient will be counted at most once per PT.

Treatment-emergent AEs (TEAEs) will be defined as:

- Any new event that starts after administration of study drug and  $\leq 30$  days after treatment discontinuation.
- Any event that was ongoing when treatment with study drug started and the severity/grade after treatment was higher than the Baseline value (fluctuations below the Baseline severity/grade are not considered as treatment emergent).
- Any new event that starts  $> 30$  days after treatment discontinuation and is assessed by the Investigator as related to study treatment.

Every effort should be made to obtain start dates for adverse events (AEs). If an AE is missing the start date, and the timing of the start date relative to treatment start is not known, it should be considered as treatment emergent for reporting and analysis purposes.

Unless otherwise stated, only TEAEs will be presented in summary tables. However, all AEs will be presented in listings.

Overall summary of safety table will include numbers and percentages of the following:

- Patients who died on study or within 30 days of last treatment
- Patients with at least 1 TEAE regardless of causality
- Patients with at least 1 treatment related TEAE
- Patients with treatment related TEAEs by worst severity
- Patients with at least 1 treatment-emergent SAE (TESAE)
- Patients with at least 1 treatment-related TESAE
- Patients who discontinued study drug due to a TEAE regardless of causality
- Patients who discontinued study drug due to a treatment-related TEAE
- Patients with a dose reduction due to a TEAE
- Patients with a dose interruption due to a TEAE

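### Protocol 10.5 lets mandated adverse-event follow-up end 30 days after last dose while 6.3.1 and 6.3.2 set no limit, and SAP 7.6.4 counts late related events that 10.5 does not require to be recorded

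*Protocol*

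**What the plan says.** **Follow-up of existing events.** Protocol 10.5 lists endpoints for follow-up of AEs and SAEs (resolution, stabilisation, consent withdrawal and others) and closes the list with "the patient is lost to follow-up or death OR until 30 days after the last dose of study drug, whichever occurs first". Its one extension is permissive and covers only ongoing treatment-related SAEs.

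Other sections carry no 30-day limit:
- 6.3.1: when a toxicity leads to interruption of one agent, or to stopping both because attribution is unclear, it is followed to resolution or baseline.
- 6.3.2: "For abnormal laboratory values that qualify as AEs, patients should be followed twice weekly until resolution or return to baseline". Non-laboratory ARRY-382 toxicities are evaluated weekly and then at least monthly.
- 7.5.2: "Clinically significant findings should be followed to resolution or stabilization".
- 10.1.2: "Laboratory abnormalities that meet the criteria for AEs should be followed until they have returned to normal or baseline". The sentence then adds Investigator discretion as an alternative.

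**Recording of new events.** Under 10.5 all AEs are recorded to 30 days after last dose. After that, "SAEs occurring greater than 30 days after the last dose of study drug should be reported only if considered related to investigational product". SAP 7.6.4 has three routes to treatment-emergent status. The third admits any new event that starts more than 30 "days after treatment discontinuation and is assessed by the Investigator as related to study treatment", with no restriction to serious events. SAP 6.0 declares no changes from the protocol.

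**Visits.** If the discontinuation visit took place 21 or more days after last dose, Protocol 8.4 says "the 30-day safety follow-up visit does not need to be performed".

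**The concern.** Characterising acute and chronic toxicity of the combination is a secondary objective in Part A and in all three Phase 2 cohorts. Two features of the plan work against it.

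First, a patient who stops treatment for an unresolved toxicity comes under two follow-up rules with different minimum endpoints. Outcome data for such events would then vary by site according to which section was applied.

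Second, the analysis plan defines a class of late events that the collection rule covers only in part. A table built on the SAP definition would look complete, but its late entries would be those judged serious plus whatever sites chose to add.

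**Working it through.** **1. Follow-up rules side by side**

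| Section | Scope | Follow to | 30-day limit |
|---|---|---|---|
| 10.5 | all AEs and SAEs | resolution, stabilisation, other endpoints | yes |
| 6.3.1 | toxicity leading to interruption or stopping | resolution or baseline | no |
| 6.3.2 | ARRY-382 toxicity; laboratory AEs | resolution or baseline | no |
| 7.5.2 | clinically significant laboratory findings | resolution or stabilisation | no |
| 10.1.2 | laboratory AEs | normal or baseline, or Investigator discretion | no |

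Stabilisation is already an endpoint in 10.5, and Investigator discretion can be exercised within it, so 7.5.2 and 10.1.2 are weak evidence. The mismatch that counts is with 6.3.1 and 6.3.2. Both cover patients whose drug is stopped, and the monthly step in 6.3.2 can run past 30 days.

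**2. New events starting after the 30-day limit**

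| Event | Protocol 10.5 | SAP 7.6.4 |
|---|---|---|
| related, serious | report | counts |
| related, non-serious | no requirement | counts |
| unrelated, serious | not reported | does not count |
| unrelated, non-serious | no requirement | does not count |

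One row of four disagrees.

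**3. Time anchors.** The protocol counts from last dose of study drug, the SAP from treatment discontinuation. I assume the latter is the disposition-page date that SAP 7.1.9.6 uses for end of treatment. If both drugs are withheld for h days before that date, required recording of all AEs ends 30 − h days after it. With h = 21, the delay in Protocol 9.2 beyond which treatment should stop unless continuing is judged in the patient's interest, this is 30 − 21 = 9 days. The SAP's first route runs to 30 days whatever the causality. For the remaining 30 − 9 = 21 days it counts non-serious events and unrelated SAEs that 10.5 does not require. If the SAP means the last-dose date, this difference vanishes.

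**4. Exposure (context only).** Protocol 5.3 sets 5.5 months for women as 30 days, and 7.5 months for men as 90 days, each "plus the time required for the investigational drug to undergo approximately 5 half-lives". Using a 30-day month and then the SAP's 30.4375 days:
- Women: 5.5 × 30 − 30 = 135 days; 5.5 × 30.4375 − 30 = 137.4 days.
- Men: 7.5 × 30 − 90 = 135 days; 7.5 × 30.4375 − 90 = 138.3 days.

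The two rules agree at about 4.5 months. ARRY-382 has a half-life of 18 to 19 hours (Protocol 2.2.2.2), so five half-lives are 3.75 to 3.96 days, and the 4.5 months must refer to pembrolizumab. Its implied half-life is 135/5 = 27 to 138.3/5 = 27.7 days. Assuming first-order decay, 2^(−30/27) = 46% to 2^(−30/27.7) = 47% remains 30 days after the last infusion, and (135 − 30)/135 = 78% of the window is still to run. If daily ARRY-382 continued 21 days beyond the last infusion, the limit falls at day 51. Then 2^(−51/27.5) = 28% remains, and (137.4 − 51)/137.4 = 63% of the window is left.

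**5. Waiver in 8.4.** A discontinuation visit on day 21 leaves 30 − 21 = 9 days without a required contact. Measured against the earliest compliant 30-day visit (day 27), the loss is 27 − 21 = 6 days. The duty in 10.5 to record AEs to 30 days stays in force.

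**The case against.** The strongest reply is that 10.5 sets a floor and forbids nothing. A site that follows an event to resolution breaches no section, and 6.3.1 and 6.3.2 are dose-modification guidance worded as recommendations. This stands against one inference a reader might draw, that a site cannot obey both rules: it can. It does not remove the point that the required minimum differs between sections.

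A reader might also infer that a late Grade 3 immune-related event managed as an outpatient has no route into the database, or that the SAP's third route can never be filled for non-serious events. The documents support neither. Section 10.4 allows an important medical event to be classed as serious on medical judgment without hospitalisation, and a related one is then reportable at any time. Nothing in 10.5 bars recording a late non-serious event; it is simply not required. What remains is late related events judged non-serious.

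A third tempting reading is that the 8.4 waiver falls mainly on toxicity discontinuations. Sections 4.1 and 7.2 let the Investigator stop treatment at first progression until repeat imaging about 4 weeks later, which can trigger the same waiver. Where attribution is clear, 6.3.1 lets the other drug continue, so the last-dose clock may not have started. Section 8.4 also permits additional safety assessments for concerns found at discontinuation.

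Finally, the exposure window comes from a contraception rule, and no section ties it to AE collection. That is correct, and it is why it carries no weight in the conclusion.

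**Conclusion.** The point holds as two inconsistencies. Within the protocol, the mandated follow-up endpoint for an unresolved toxicity is at most 30 days after last dose in 10.5 and unlimited in 6.3.1 and 6.3.2. Between the documents, SAP 7.6.4 counts late related events of any seriousness while 10.5 requires only the serious ones, and the clocks start from differently named dates. Late treatment-emergent counts would therefore be incomplete and weighted to serious events, and outcomes of unresolved toxicities could be cut off differently by site.

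The Phase 2 primary endpoint, ORR, is not affected. A reader might infer that reported immune-related toxicity will look better than it is by some known amount. The documents give no late-event rate, so only the direction for late non-serious related events can be stated. The 4.5 months is inferred, and the documents state no pembrolizumab half-life.

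One limitation applies throughout: the SAP was written to protocol Version 5 (02 January 2019), and the protocol read here is Version 4. Whether Version 5 changed 10.5 could not be checked.

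**What to change.** 1. Check 10.5 in protocol Version 5 first; the items below apply if it is unchanged.
2. Reconcile 10.5 with 6.3.1 and 6.3.2 so that one stated follow-up endpoint applies to treatment-related AEs and to AEs leading to discontinuation. The sponsor should choose the endpoint and any duration.
3. Align collection with the SAP's third route, in one of two ways. Either record related non-serious AEs after 30 days at contacts already scheduled, or restrict that route to related SAEs and state the limitation in the report. Collection needs both the 8-weekly progression visits (8.5) and the 3-monthly survival contacts (8.6). Survival contacts begin only after progression follow-up ends, so on their own they would miss patients who stop for toxicity without progression.
4. Use one time anchor in both documents, and define it.
5. Where the 8.4 visit is waived, confirm AE status to 30 days after last dose by telephone.

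The cost is wording in two documents, an AE question at existing contacts and a call in waived cases, with no new patients or procedures. The drawbacks are some extra AE entries and late events that are harder to attribute, particularly after subsequent therapy. Restricting the SAP route instead costs nothing in collection but gives up information on late non-serious toxicity.
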